9.3.4.1 Pharmacokinetics for Oral Dosing

Samples will be drawn from all participating subjects at the Lead-in End Visit in order to define the steady-state pharmacokinetic profile of the respective, stable dosing regimen on oral atorvastatin.

The subject is directed to refrain from taking their daily oral dose of atorvastatin at home, but then to bring the dose to the clinic for the PK visit. The visit is scheduled such that the dose is taken in the clinic at a time of day as close as possible to the time that the subject typically takes their oral dose.

At the oral PK visit, samples are drawn and processed per the procedure detailed above in [Section 9.3.4](#) at the following times; allowable windows are listed in [Table 9-3](#):

- Within 60 minutes prior to taking the oral dose of atorvastatin.
- At the following times after taking the oral dose:
 - 30 minutes
 - 1 hour
 - 2 hours
 - 4 hours
 - 6 hours
 - 8 hours

Levels of atorvastatin and metabolites measured from the pre-dose timepoint are imputed as the Hour 24 levels since the subject is on daily, constant dosing.

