9.3.4.2 Pharmacokinetics for Multi-dose Intravenous or Subcutaneous Dosing (Treatment Phase)

Subjects receive their last dose of injectable atorvastatin at their Day 15 visit. Following the sampling and processing procedure detailed in [Section 9.3.4](#), samples are drawn at the following times relative to their last injectable dose; allowable windows are listed in [Table 9-3](#):

- Within 60 minutes prior to the start of the dose.
- At the following times after completing the dose:
 - Immediately after completion (**IV dose only**; subjects taking the SC dose under Amendment 03 omit this timepoint.)
 - 30 minutes
 - 1 hour
 - 2 hours
 - 4 hours
 - 6 hours
 - 8 hours

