4.5 Data Handling

All subject data used for analysis will be displayed in listings.

Summaries for continuous variables will include the descriptive statistics for number of subjects (n), mean (arithmetic and geometric), standard deviation (SD), minimum (min), median, and maximum (max). Summaries for categorical (discrete) variables will include the number and/or percentage of subjects in a particular category.

Conventions for presentation of numerical data:

Minimum and maximum values will be presented to the same number of decimal places as the electronic Case Report Form (eCRF) data. Means and medians will be presented to one more decimal place than the eCRF data. Standard deviations will be presented to two more decimal places than the eCRF data.

Plasma concentration and PK parameters in tables and listings will be displayed with 3 significant figures as follows:

- (1) Values ≥ 0.0001 and < 1 will be reported with 3 significant figures (e.g., 0.0123).
- (2) Values ≥ 1 and < 10 will be reported with 3 significant figures (e.g., 1.02).
- (3) Values ≥ 10 and < 100 will be reported with 3 significant figures (e.g., 10.2).
- (4) Values ≥ 100 and < 1000 will be reported with 3 significant figures (e.g., 102).
- (5) Values ≥ 1000 will be reported with 3 significant figures (e.g., 1020).
- (6) Values = 0 will be reported as 0.

Values for T_{max} will be reported to 2 significant figures.

In the evaluation of both oral and injectable, multiple-dose PK, levels of atorvastatin and its metabolites measured from the pre-dose timepoint are imputed as the Hour 24 levels since the subject will have been on at least a two-week period of daily, constant dosing, and the pre-dose value will essentially be the Hour 24 level from the previously administered dose. This will relieve subjects from making an extra clinic visit.

Baseline is defined as the last value measured prior to the first dose of study drug.

Change from Baseline is defined as [Post-baseline Value – Baseline Value].

5 Data Analysis

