5.7.2 Pharmacokinetic Parameters

Pharmacokinetic parameters will be derived for atorvastatin and its metabolites for subjects in the PK population.

Pharmacokinetic parameters are defined in Table 4.

Table 4: Pharmacokinetic Parameters

Parameter	Description
C_{\max}	Maximum plasma concentration
AUC_{0-24}	Area under the plasma concentration-time curve from time zero to 24 hours
AUC_{∞}	Area under the plasma concentration-time curve from time zero to infinity
T_{\max}	Time to reach maximum plasma concentration
$T_{1/2}$	Elimination half-life
K_{el}	Elimination rate constant
$Cl(/F)$	(Apparent) clearance of drug from plasma for extravascular dosing
VD_{ss}	Volume of distribution at steady state for intravenous dosing
V_z/F	Apparent volume of distribution for extravascular dosing

Pharmacokinetic parameters will be calculated using noncompartmental methods and actual blood sampling times. In case of missing actual time, planned (or nominal) time will be used.

Concentration listed as below the limit of quantitation will be set to zero for the calculations. If a sample is missing or the value is not reportable and is between two measurable concentrations, the value at that time point will be left blank for the analysis and reported as either Not Reportable (NR) or No Sample (NS).

The PK timepoint at 24-hour post oral dosing is the pre-dose concentration due to reaching steady state. The first timepoint immediately following IV bolus dosing is set as 0.0055 hour (assume 20 seconds bolus dosing). The 24-hour post-dose concentration is set as pre-dose concentration before IV and multiple-dose SC dosing. For the single dose SC (sub-study) the pre-dose concentration is the 24-hour post-oral dose concentration.

No value of K_{el} , AUC_{∞} or $t_{1/2}$ will be reported for cases that do not exhibit a terminal log-linear phase in the concentration versus time profile. If the adjusted R-squared value ($Rsq_{adjusted}$) is < 0.8 , the analyst may evaluate if other time points are more appropriate and use those for the calculation of K_{el} , or no value of K_{el} , AUC_{∞} or $t_{1/2}$ will be reported.

For determination of AUC_{∞} , if calculated AUC from last to infinity is greater than 20% of the calculated AUC from 0 to infinity, then AUC_{∞} will not be reported.

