5.7.3 Relative Bioavailability Analysis

To compare the PK profile of atorvastatin and metabolites administered by the IV or SC route to that of oral administration, the relative bioavailability analysis will be performed for each cohort using key PK parameters (C_{max} , AUC_{0-24} and AUC_{inf}) of atorvastatin and, if data allow, its metabolites. Dose-normalized key PK parameters of the oral and IV (or SC) routes of administration will be log-transformed and analyzed using an analysis of variance (ANOVA) model including terms for treatment route as a fixed effect and subject as a random effect. The least squares geometric means ratio of atorvastatin oral vs IV (or SC) will be calculated. A 90% CI on the ratio of untransformed PK parameters will be derived through reverse transformation of the 90% CI for the difference in the log scale to the 90% CI for the ratio in the original scale.

When appropriate, the same analysis may be performed to compare the PK profile of the atorvastatin SC vs oral (Cohort 4).

The least-squares geometric means, ratio of the geometric means and 90% CIs on the ratio will be displayed.

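### AUCinf taken from steady-state profiles is a key parameter in the oral versus IV/SC bioavailability ANOVA, although it counts drug left from earlier doses; AUC0-24 should carry the comparison

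*SAP*

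**What the plan says.** SAP 5.7.3 compares oral with IV (or SC) dosing and states that "the relative bioavailability analysis will be performed for each cohort using key PK parameters". It gives these as "key PK parameters (C_{max} , AUC_{0-24} and AUC_{inf}) of atorvastatin" and, if the data allow, its metabolites. The parameters are dose-normalised, log-transformed and analysed in an ANOVA with route fixed and subject random. Each yields a geometric mean ratio with a 90% CI. No acceptance limits are given.

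Both profiles come from repeated daily dosing. Protocol 9.3.4.1 samples the oral dose at the Lead-in End Visit "in order to define the steady-state pharmacokinetic profile of the respective, stable dosing regimen on oral atorvastatin". For the injectable route, Protocol 9.3.4.2 states: "Subjects receive their last dose of injectable atorvastatin at their Day 15 visit". Sampling follows that dose. SAP 5.1 builds the Bioavailability Population on the multiple-dose IV or SC profiles, so the single-dose SC sub-study is not part of this comparison.

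The SAP relies on steady state. Section 4.5 gives as its reason that "the subject will have been on at least a two-week period of daily, constant dosing", and section 5.7.2 says "The PK timepoint at 24-hour post oral dosing is the pre-dose concentration due to reaching steady state". The same substitution is made for IV and multiple-dose SC.

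Table 4 in SAP 5.7.2 defines AUCinf as "Area under the plasma concentration-time curve from time zero to infinity". It has no correction for residual drug and no restriction to single-dose profiles. AUCinf is not reported when the part beyond the last point "is greater than 20% of the calculated AUC from 0 to infinity". Table 4 lists clearance without a formula.

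**The concern.** After a single dose, AUCinf is the whole exposure from that dose, and dividing it by the dose is sensible. At steady state with linear kinetics, AUC0-24 already equals the whole exposure from one dose. Extrapolating the same profile to infinity adds what earlier doses left in the body. Normalising by a single dose does not remove that excess.

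The excess cancels from the oral/injectable ratio only if it is the same proportion of AUC0-24 on both routes. The plan does not state this as an assumption or set a formal check of it. Protocol 5.4 expects parent-to-metabolite ratios to change with IV dosing, and metabolites may enter the same ANOVA, so equal profile shapes cannot be taken for granted.

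At stake is one of the three ratios that the SAP calls key, with its 90% CI. It could differ from the AUC0-24 ratio for reasons unrelated to bioavailability.

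**Working it through.** The plan states no figure for this analysis, so there is none to reproduce.

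**Inputs from the documents.** Dosing interval 24 h. The 24 h concentration is set equal to the pre-dose trough on both routes (SAP 5.7.2). AUCinf is withheld when more than 20% of it is extrapolated (SAP 5.7.2).

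**Assumed.** Linear kinetics and, for the figures, one compartment with bolus input. The documents give no half-life by route, so a range is shown.

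**Step 1, general result.** By superposition at steady state, AUC0-24 equals single-dose AUCinf. Extrapolating from the 24 h point gives

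AUCinf = AUC0-24 + Ctrough/kel,

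so the inflation over exposure per dose is R = 1 + Ctrough/(kel × AUC0-24). The false factor in the ratio is R(oral)/R(injectable). It is 1 exactly when Ctrough/(kel × AUC0-24) is equal on the two routes.

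**Step 2, one compartment.** The extrapolated share is f = exp(−24 ln 2/half-life), and R = 1/(1 − f).

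| Half-life | f | R |
|---|---|---|
| 2 h | 0.0002 | 1.0002 |
| 3 h | 0.0039 | 1.0039 |
| 5 h | 0.0359 | 1.0372 |
| 7 h | 0.0929 | 1.1024 |
| 10 h | 0.1895 | 1.2338 |

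**Step 3, false factor in the oral/injectable ratio.**

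- oral 3 h, injectable 2 h: 1.0039/1.0002 = 1.004
- 7 h and 5 h: 1.1024/1.0372 = 1.06
- 10 h and 7 h: 1.2338/1.1024 = 1.12
- 10 h and 5 h: 1.2338/1.0372 = 1.19
- equal half-lives: 1.00

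Swapping the routes gives the reciprocals.

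**Step 4, effect of the 20% rule.** If the 24 h value is quantifiable, f ≤ 0.20 means R ≤ 1/(1 − 0.20) = 1.25, whatever the compartment model. With both routes reported, a subject's ratio is off by a factor between 1/1.25 = 0.80 and 1.25. In the one-compartment model the rule corresponds to a half-life of at most 24 ln 2/ln 5 = 10.3 h. Profiles beyond that lose AUCinf but keep AUC0-24 and Cmax.

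**Step 5, profile shape.** Half-life alone does not settle the bias.

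- With a 7 h half-life on both routes, first-order oral absorption (rate 2 down to 0.25 per h) against a one-compartment bolus shifts the ratio by 0.5% to 5.7%.
- With 7 h on both routes, oral absorption at 1 per h against a two-compartment IV profile (distribution half-life 0.5 h, 80% down to 30% of AUC in the terminal phase) shifts it by 3% to 8%.
- Conversely, oral at 7 h with absorption 1 per h has R = 1.114. A two-compartment IV profile with half its AUC in the terminal phase has the same R at about 9.9 h, so unequal half-lives then give no bias.

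**Step 6, AUC0-24 instead.** The accumulation factor is 1.00 on both routes, so the false factor is 1.00 for any pair of half-lives.

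**The case against.** The strongest reply is that nothing turns on this ratio. AUC0-24 is in the same ANOVA, no equivalence limits are set, and dose adjustment and cohort success rest on lipid values (Protocol 9.3.6.2.2 and 12.3.2, SAP 5.6). That stands, and it limits the harm to interpretation.

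The size is also uncertain. Every half-life above is assumed, and at 3 h against 2 h the effect is 0.4%. If the trough is below quantitation, carry-over is minimal. The last measurable point is then at most 8 h, and the 10.3 h threshold does not apply. Half-life and kel will be listed by subject and treatment, so a route difference would be visible beside the ratio. All of this stands, although a listing does not correct the ratio.

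A reader might infer more than the documents support:

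- **A bias of 30% or more.** A 14 h oral half-life gives R = 1.438, and against 7 h a factor of 1.438/1.102 = 1.30. But its extrapolated share is 30.5%, so the SAP would not report that AUCinf.
- **Bias whenever half-lives differ.** Step 5 shows that differing half-lives can cancel and equal ones can leave bias. The condition is the one in step 1.
- **Clearance understated by the same factor.** This would follow only if clearance were dose/AUCinf, and no section says so. What can be said is that the formula is missing.

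Finally, AUCinf cannot simply be removed, because Protocol 7 and SAP 3 list it among the parameters to be calculated. That is a fair limit on the remedy.

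**Conclusion.** The point holds in a limited form. AUCinf from a steady-state profile is not exposure per dose, and the plan uses it as a key parameter on both sides of the comparison without correction. In the one-compartment examples the ratio is distorted by between 0.4% and 19%. Any reported pair with quantifiable troughs lies between factors of 0.80 and 1.25. The mechanism rests on linear kinetics and on the SAP's own steady-state premise; the size rests on assumed half-lives and cannot be fixed from the documents.

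The 20% rule limits the error without removing it, and it brings selection. With 13 subjects in each IV cohort and 10 in the SC cohort, losing AUCinf on one route breaks that subject's within-subject comparison, so the AUCinf and AUC0-24 ratios may rest on different subjects. If they disagree, a reader could not separate bias, selection and a real route difference. The change is worth making for a clear report; no trial decision is at risk.

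**What to change.** 1. In SAP 5.7.3, base the steady-state oral versus IV/SC ANOVA on Cmax and AUC0-24 only, for atorvastatin and for any metabolites analysed.
2. Keep AUCinf from steady-state profiles as a listed and summarised descriptive parameter, so that the endpoint lists in Protocol 7 and SAP 3 are still met.
3. In SAP Table 4, state that steady-state CL (IV) and CL/F (oral, multiple-dose SC) are dose/AUC0-24.

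The cost is SAP wording. No new data or procedures are needed, since Cmax and AUC0-24 are already planned. The small downside is that one planned AUCinf ratio and its 90% CI give way to descriptive summaries.

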5.7.4 Exploratory Dose Response

An exploratory dose response analysis may be conducted if the efficacy data vs the dose indicates a trend. Summary of the baseline, Day 8 and Day 15 for LDL-C and HDL-C by IV dose will be produced. A dose-response plot (mean change from baseline in LDL-C and HDL-C for Day 8 and Day 15 vs. IV dose) may be produced. If the efficacy over time vs IV dose indicates a trend then a plot of percent change from baseline for LDL-C and HDL-C at Days 8 and 15 vs IV dose may be produced.

5.8 Safety Analysis

The safety and tolerability of IV and SC atorvastatin will be assessed by the evaluation of TEAEs, study discontinuation information, laboratory test results, and vital signs.

Safety variables will be tabulated and presented for all subjects in the Safety Population. Data will be summarized by cohort and by route. Adverse events will be summarized by MedDRA system organ class (SOC), preferred term (PT) and treatment. Mean change (baseline to Day 15) for CPK, ALT and AST in each dosing cohort, changes from baseline in other clinical laboratory parameters and vital signs parameters will be summarized.

5.8.1 Study Product Exposure

Exposure to study drug will be listed by cohort, subject and treatment received, indicating dose date and time. Any deviations will be documented.

5.8.2 Adverse Events

Adverse events will be collected from the ICF signing to last subject contact/visit/end of post-treatment follow-up period.

All AEs will be coded and classified according to MedDRA (Version 22.0). The intensity of adverse events is judged by the Investigator as mild, moderate or severe, and a causal relationship to study drug is judged by the Investigator as related, probably related, unlikely related or not related. Adverse events occurring prior to the date and time of first dose of study drug are considered non-TEAEs. Events occurring on or after the date and time of the first dose of study drug through last contact/visit of follow-up are considered treatment emergent if they are not listed in the subject's history.

A summary table of AEs will be created containing: number of AEs, number of subjects experiencing AEs, number of TEAEs, number of subjects experiencing TEAEs, severe TEAE, serious AEs, serious TEAEs, AEs causing discontinuation and AEs causing death.

All TEAEs will be summarized as the number and percentage of subjects by SOC, PT and treatment. Separate summaries will be created by intensity and by relationship to study drug. If the same AE (PT) is reported more than once for the same subject, it will only be counted once in the summary table. For summary tables by intensity and relationship to study drug, if the same AE (PT) is reported more than once for the same subject, the highest intensity grade (severe > moderate > mild) or the strongest relationship to treatment (related > probably related > unlikely related > not related) will be counted in the summary table.

All AEs will be listed, and a flag will indicate if the AE is treatment emergent.

All serious AEs (SAEs) will be listed, and a flag will indicate if the SAE is treatment emergent.

All adverse events leading to study discontinuation will be listed by subject.

All adverse events leading to death will be listed by subject.

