9.4 Measurements and Evaluations

9.4.1 Description of Screening Visit

Before the initiation of study-specific screening assessments, the subject or legal authorized representative must be given a complete explanation of the purpose and conduct of the study. Subsequently, the subject or legal authorized representative must sign and receive a copy of an Informed Consent Form that was approved by the center's governing Institutional Review Board (IRB).

During this consenting process, the Investigator or designee has a preliminary discussion with the subject about participation in the sub-study. The subject's initial consent or refusal to participate in the sub-study is documented; however, this decision by the subject can be re-evaluated and changed prior to the end of the study treatment period.

Subjects that enter the study taking oral statins remain on their prescribed dose during the screening process.

After consent is obtained, the inclusion criteria in [Section 8.4.1](#) are confirmed, including the measurement of LDL-C by the point-of-care test (CardioChek® PA Analyzer, or equivalent). In the event that the point-of-care analyzer gives an error message rather than a numerical result at the Screening Visit, a blood sample may be submitted to the site's local laboratory for the eligibility determination. Subjects that do not meet the eligibility requirement are deemed screen failures; others continue to complete the full screening visit to determine the subject's eligibility to enter the Lead-In Period and to document their baseline disease state. Allowable time windows are described in [Table 9-1A](#) and [Table 9-1B](#):

- Collection of demographic data, including age, gender, race and ethnicity

- Review and documentation of medical history. Resolved diseases or past procedures that are not significant to the disease under study should be captured only if they occurred or were present in the previous five years. Other history (diagnoses, major signs or symptoms) should be recorded in the CRF regardless of time reference.
- A serum and/or urine pregnancy test is performed on all women.
- A serum FSH and estradiol test may be performed by Investigator on subjects to confirm postmenopausal status.
- Serology for HIV, HBV, and HCV.
- Urine Drug Screen and Saliva Alcohol Test
- A baseline physical examination is performed on all significant body systems.

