12.3.6 Safety Analyses

The safety and tolerability of Atorvastatin IV and SC will be assessed by the evaluation of treatment-emergent adverse events (TEAEs), study discontinuation information, laboratory test results, vital signs and physical examination findings.

Safety variables will be tabulated and presented for all subjects in the Safety Population. Data will be summarized by route and cohort. Adverse events will be coded using the Medical Dictionary for Regulatory Activities (MedDRA) for preferred term and system organ class, and will be listed by subject. Treatment-emergent AEs (TEAEs) will be summarized by treatment, where treatment-emergent is defined as any event with a start date on or after the date and time of the first dose date and time of study drug. All TEAEs will be summarized by relationship to study drug and by intensity.

Deaths, SAEs, and AEs resulting in study discontinuation will be listed.

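### SAP 5.8.2 adds an undefined medical-history condition to the protocol's TEAE definition, so an adverse event that starts on drug can be left out of the TEAE counts and tables (minor)

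*SAP*

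**What the plan says.** Protocol 12.3.6 defines a treatment-emergent event as "any event with a start date on or after the date and time of the first dose date and time of study drug". It sets no other condition.

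SAP 5.8.2 uses two sentences. The first reads: "Adverse events occurring prior to the date and time of first dose of study drug are considered non-TEAEs". The second takes "Events occurring on or after the date and time of the first dose of study drug", up to the last follow-up contact, and says that these "are considered treatment emergent if they are not listed in the subject's history".

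SAP 5.8.2 then builds its main safety tables on the resulting flag: "All TEAEs will be summarized as the number and percentage of subjects by SOC, PT and treatment". It specifies separate TEAE summaries by intensity and by relationship to study drug, and the overview table counts TEAEs, severe TEAEs and serious TEAEs. The same section also provides a listing of everything: "All AEs will be listed, and a flag will indicate if the AE is treatment emergent".

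**The concern.** The history condition appears in the SAP and not in the protocol. Taken at its word, it is a rule of exclusion: an event can begin after dosing and still be denied TEAE status because of what the subject reported at screening. The clause leaves three things open:

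- the level of matching (verbatim term, preferred term or broader condition);
- whether resolved history counts as well as ongoing history;
- whether a recurrence or worsening is exempt.

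Two programmers could therefore derive different flags from the same records, and neither flag need agree with the protocol. At stake are the TEAE counts and the only breakdowns by intensity and causality that SAP 5.8.2 specifies.

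There is a second, separate difference. The SAP speaks of events occurring where the protocol speaks of a start date. That leaves unclear how to class an event that starts in the lead-in and continues past the first dose.

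**Working it through.** No figure in the plan needs reproducing. The check sets the passages side by side and tests them on two cases.

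**How wide the history net is.** Protocol 9.4.1 limits resolved diseases and past procedures that do not matter to the disease under study: they "should be captured only if they occurred or were present in the previous five years". Other diagnoses and major signs or symptoms go into the CRF with no time limit. A recorded history can therefore hold many terms that might later appear as adverse events. Protocol 5.5 names arthralgia and pain in extremity among the common reactions reported with oral atorvastatin, and both could plausibly be in a subject's history.

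**Case 1: history lists arthralgia, and a new arthralgia starts on Day 5.**
- Protocol 12.3.6: the start is after the first dose, so it is a TEAE.
- SAP 5.8.2, ordinary reading: the event falls in the window but is listed in the history, so it is not a TEAE. It leaves the TEAE counts and the SOC/PT, intensity and relationship tables.

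**Case 2: an event starts in the lead-in and is still present after the first dose.**
- Protocol 12.3.6: the start is before the first dose, so it is not a TEAE.
- SAP 5.8.2: if occurring means present, the event fits both sentences, and it need not be in the history. If occurring means starting, it is not a TEAE. The text does not say which is meant.

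The omission in Case 1 comes from the history clause alone. The word in Case 2 works in the other direction: at most it lets in, or leaves undecided, an event that began before dosing.

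**Is the clause needed to keep out background conditions?** No. Protocol 11.1.1 already says that pre-existing conditions found by screening procedures are not adverse events. A start-date rule also excludes anything that began before dosing and merely continues. Protocol 11.1.2, by contrast, includes re-emergence or worsening relative to the pretreatment baseline among its anticipated events, so a recurrence is something the protocol expects to see as an event.

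**Is the departure declared?** SAP 5.11, on changes from pre-specified analyses, has a heading and no text. SAP 5.12 concerns later deviations from the SAP itself.

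**Weight of one reclassified subject**, as the shift in one term's incidence = 1/n:

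| Denominator | Source | Shift |
|---|---|---|
| Planned IV cohort, n = 13 | SAP Table 1 | 1/13 = 7.7 points |
| SC cohort, n = 10 | SAP Table 1 | 1/10 = 10.0 points |
| Three planned IV cohorts, n = 3 × 13 = 39 | SAP Table 1; summary by route in SAP 5.8 | 1/39 = 2.6 points |

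The safety population also keeps subjects treated at a dose that was later abandoned, so actual denominators may be larger and the shifts smaller. These figures show what one subject weighs. They do not estimate the effect.

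**The case against.** The best defence is that the clause was meant narrowly. It speaks of events listed in the history. History is taken at screening, so a new episode on Day 5 cannot literally be listed there. On that reading the clause only removes pre-existing conditions, and what is missing is a matching rule. This is a fair account of the likely intent. It does not rescue the text, because on that reading the clause has nothing left to do: the protocol's AE definition and a start-date rule already cover those conditions. A programmer given the sentence would most naturally compare AE terms with history terms, which produces Case 1.

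A second objection is that the two SAP sentences read naturally as a before/after split, so that occurring just means starting. That is reasonable, and it is why the wording is only a secondary ambiguity. A reader might infer that this word also helps push on-drug events out of the tables. The documents do not support that.

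A reader might also infer that the rule hides safety information. It does not:

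- Affected events stay in the all-AE listing without the TEAE flag, in the overall AE and SAE counts, and in the SAE, discontinuation and death listings where they qualify.
- SAP 5.8 also says "Adverse events will be summarized by MedDRA system organ class (SOC), preferred term (PT) and treatment", which could be read as an all-AE table, although without the intensity and relationship breakdowns and with events from consent onward mixed in.
- The CPK, ALT and AST summaries are untouched.
- A history of myopathy or rhabdomyolysis excludes a subject at lead-in (Protocol 8.4.2.2).
- Safety is reported descriptively, and no decision rule uses TEAE counts. The review before a dose increase (Protocol 9.3.6.2.2) uses serum biochemistry.

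All of this stands, and it keeps the point minor.

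**Conclusion.** The point holds as a conflict between a stated SAP rule and the protocol definition, with severity minor. As written, SAP 5.8.2 can remove an adverse event that starts on drug from the TEAE, severe-TEAE and serious-TEAE counts and from the TEAE tables, when the subject's history lists the same condition. The change is not declared in SAP 5.11. The start-date wording is a separate, lesser ambiguity about events that begin in the lead-in.

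The conclusion rests on the ordinary reading of the history clause, namely that an event is matched to the history by condition or term. The number of events affected cannot be derived, because the documents give no adverse event or history frequencies, and it may be zero. A claim that the safety results are materially understated would go beyond the documents.

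**What to change.** Replace the two classification sentences in SAP 5.8.2 with wording to this effect:

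*AEs with a start date and time before the first dose of study drug are non-TEAEs. AEs with a start date and time on or after the first dose, up to the final follow-up contact, are treatment emergent, whether or not the condition is listed in the medical history.*

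This restores the protocol's test, settles the lead-in case and removes the need for a matching rule. No separate worsening rule should be added. Protocol 11.1.2 has the investigator record maximum severity, and the documents describe no worsening date for an AE, so such a rule could not be derived reliably and would conflict with the start-date test. A worsening entered as its own AE record is classed by that record's start date. A worsening never entered as an AE is not recovered.

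Optionally, flag in the AE listing those events whose preferred term also appears in the coded history. SAP 5.4 and 5.8.2 both specify MedDRA 22.0, so this is straightforward.

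Cost: two sentences and one derived flag, using records already collected. The downside is slightly higher TEAE counts, some of them recurrences of background conditions. The optional flag lets a reader see which. If the sponsor prefers to keep a history condition, the SAP should state the match level, the treatment of resolved history and of recurrence or worsening, and declare the departure in SAP 5.11.
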